#### **3.3. Design**

The purpose of this study is to evaluate the safety and effectiveness of the Spatz3 in subjects with a BMI  $\geq 30$  and  $< 40$  who have failed to achieve and maintain weight-loss with a weight control program.

Subjects will be studied in a randomized, controlled, multi-center study. The control group will receive dietary/exercise counseling for 32 weeks. The treatment group will receive dietary/exercise counseling plus the Spatz3 balloon for 32 weeks.

The study will run 32 weeks for the control group and 32 weeks followed by a 24-week follow up period for the treatment group.

282 eligible subjects will be randomized to treatment (188 subjects) or control (94 subjects) arms. All treatment group subjects will undergo endoscopy and those without endoscopic contraindications will be implanted with the Spatz3 balloon for 32 weeks. All subjects will follow a 1000-1200 kcal/day-deficit diet during their participation in the study.

At 18 weeks  $\pm$  4 weeks, treatment arm subjects will be evaluated, and those that meet the criteria described below in section 4.3.3.2.4 will undergo an adjustment procedure wherein the balloon volume will be increased to achieve extra weight loss. The balloon adjustment procedure is done with an endoscopy procedure under the same sedation as the implantation procedure. At the end of the 32-week treatment period the control subjects will be dismissed and the treatment group will be explanted and will have a 24-week follow up.

### **3.4. Study Setting**

The study will be conducted at up to 10 US centers. The maximum enrollment at each site will be limited to 65 subjects.

### **3.5. Subjects**

Participants will be adult patients (22 years of age or above) with a BMI  $\geq 30$  and  $<40$  that meet the eligibility criteria below. All eligibility criteria must be met at the time of randomization.

#### **3.5.1. Inclusion Criteria**

1. Age 22 - 65
2. BMI  $\geq 30$  and  $<40$
3. Willingness to comply with the substantial lifelong dietary restrictions required by the procedure
4. History of obesity (BMI  $\geq 30$ ) for at least 2 years
5. History of failure with non-surgical weight loss methods
6. Willingness to follow protocol requirements, including signed informed consent, routine follow-up schedule, completing laboratory tests, completing diet counseling
7. Residing within a reasonable distance from the investigator's office and able to travel to the investigator to complete all routine follow-up visits
8. Ability to give informed consent
9. Women of childbearing potential (i.e., not post-menopausal or surgically sterilized) must agree to use adequate birth control methods. Acceptable birth control methods are limited to hormonal contraceptives (oral, flexible vaginal ring, skin patch, injection), diaphragms, IUDs, condoms with or without spermicide, and voluntary abstinence. The method of birth control must be documented and verified at follow-up. Should a treatment arm subject become pregnant during the implantation period, the balloon will be extracted during the second trimester - the timing of which will be determined via consultation with the subject's obstetrician.

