**Figure 1: Study Timeline**

#### 4.3.1. Screening and Eligibility Assessment

Screening will be conducted by the investigator or co-investigator and documented on the PI Intake form (*Appendix E2: CRF\_2 PI Intake*) and Screening Labs form (*Appendix E3: CRF\_3 Screening Labs*). Screening must occur no more than 30 days prior to implantation.

Screening will include the following:

1. Screening exam by investigator or co-investigator (*Appendix E2: CRF2\_PI Intake*). Includes Medical history, Current medications, Record contraceptive method for female subjects, Vital signs, Body Weight and Height, Physical exam, Evaluation of inclusion/exclusion criteria.
2. Sign Informed Consent Form (*Appendix A: Informed Consent*)
3. Dietician intake - Baseline body weight, height, ideal body weight, excess weight, BMI, (*Appendix E5: CRF5\_Dietician Intake*)
4. Laboratory tests\* plus EKG
5. Psychological evaluation (*Appendix E10: CRF10\_Consultation with Psychologist*)
6. Diabetic subject – follow up by provider or PI (*Appendix E11: CRF11\_Diabetic Patient Follow Up*)

\*Laboratory Tests (*Appendix E3: CRF3\_Screening Labs*) include:

CBC: Hgb, Hct, WBC, MCV, platelets

Chemistry panel: sodium, potassium, chloride, CO2, BUN, creatinine, glucose, SGOT/AST, SGPT/ALT, alkaline phosphatase, total bilirubin, total protein, albumin, total cholesterol, Fe/TIBC, B12, Folic Acid, 25-Hydroxy Vitamin D, TSH

Coag: Pro Time or INR, PTT

Urinalysis

HgbA1c (if diabetic)

H. Pylori Serology

Within 1 week of the screening tests, the PI will review the results and determine eligibility of the subject. The center will inform the subject of their results within 10 days of the tests. All potential subjects who pass the initial screening assessment must return for an additional visit within 7 days of the scheduled implantation procedure for the Pre-Implantation visit (*Appendix E4: CRF4\_Preimplantation Tests and Data*). This will include an assessment of the following:

- Urine pregnancy test (women of child-bearing potential)
- Medications List
- Weight (Note: This is the baseline weight that will be used for the endpoint assessments)

Subjects with a positive pregnancy test or who are taking medications listed in the exclusion criteria will be excluded from the study at this time, and will be considered to be screening failures.

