### *4. 18- week adjustment*

At 18 weeks ± 4 weeks, all treatment arm subjects whose balloon has not been removed will be evaluated to determine if an upward adjustment is clinically appropriate. The following algorithm will be followed:

1. Subjects who have reached goal weight (calculated by BMI of 25) **and** are without any symptoms of gastroesophageal reflux or symptoms suggestive of gastritis or gastric ulcer, will not receive a balloon volume adjustment, and endoscopy at 18± 4 weeks will not be performed.
2. Subjects who underwent a prior unscheduled endoscopy with findings of a gastric ulcer will not receive an adjustment at 18± 4 weeks and no additional endoscopy beyond that described in section 2 above will be performed.
3. For all other subjects, endoscopy will be performed, and adjustments/treatment decisions will reflect the following algorithm:
  - a. For subjects with gastric ulceration found at endoscopy, **no upward adjustment** and PI will decide if balloon requires extraction based on endoscopic findings as described below.

Subjects who present with an endoscopically confirmed gastric ulcer will be treated as follows:

- **Ulcers whose smallest dimension (S) is  $\geq 2$ cm, or if there are any stigmata of increased risk of bleeding, such as visible vessels or clots**

The balloon should be extracted. Biopsy for H.pylori will be performed and treatment prescribed if positive.

These subjects should be treated with the following regimen: with sucralfate 1,000 mg PO Qid, and PPI medication twice daily for 3 months, followed by endoscopic evaluation after 3 months to confirm healing.

- **Ulcers whose smallest dimension (S) is  $\geq 1$  cm and  $< 2$  cm**

The balloon volume should be decreased by 150 ml (or 100 ml if starting volume is 400 ml) and subjects should be treated with the following regimen: sucralfate 1,000 mg PO Qid and increasing PPI medication to twice daily for 2 months. A biopsy for H.pylori will be taken and treatment prescribed if positive.

Endoscopic follow up will be performed at 8 weeks and if not healed at 8 weeks, an additional endoscopy at 16 weeks to confirm healing.

- At the 8-week follow-up, if signs of healing defined by a 25% reduction in either length or width are not observed, then the balloon should be extracted.

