#### 4.3.4. Follow-Up Schedule

Follow-up visits for treatment and control patients will occur according to the following schedule: Visits at 1 week, 2 weeks, and 4 weeks ( $\pm$  3 days), and thereafter every 4 weeks ( $\pm$  2 weeks) until primary endpoint assessment at 32 weeks. In addition, 1-2 weeks after the adjustment procedure the subject will have a follow up appointment with the PI/NP.

Each follow-up visit will include:

1. Clinical assessment by PI or nurse practitioner or physician’s assistant for both the treatment group and control group (*Appendix E6: CRF6\_Control Group PI Follow Up* or *Appendix E7: CRF7\_Treatment Group PI Follow Up*)
2. Satiety and Dietary Assessment for both the treatment group and control group - limited to 30-45 minutes per session (*Appendix E8: CRF8\_Control Group Dietician Follow Up* or *Appendix E9: CRF9\_Treatment Group Dietician Follow Up*)
3. Record adverse events, device complications, concomitant medication (*Appendix E6: CRF6\_Control Group PI Follow Up* or *Appendix E7: CRF7\_Treatment Group PI Follow Up*)
4. Weight to be done by staff (patient may not speak with weighing personnel and may not disclose if they are control or treatment arm)

Control patients will exit the study at Week 32. Treatment patients will have the device explanted and will be followed for an additional 24 weeks according to the following schedule: Visits at Week 36 ( $\pm$  3 days) and thereafter every 4 weeks ( $\pm$  2 weeks) until 56 weeks. Treatment patients who undergo balloon extraction prior to 32 weeks will be followed from the time of balloon extraction an additional 24 weeks according to the following schedule: Visits at 4 Weeks post extraction ( $\pm$  3 days) and thereafter every 4 weeks ( $\pm$  2 weeks) until 24 weeks after the extraction.

These follow-up visits for the treatment group only, will include:

1. Clinical Assessment - only at the visit 4 weeks post extraction(*Appendix E7: CRF7\_Treatment Group PI Follow Up*)
2. Satiety and Dietary Assessment (*Appendix E9: CRF9\_Treatment Group Dietician Follow Up*)

A summary of required visits and procedures for subjects who do not require an unscheduled endoscopy is shown in the following table and provided in *Appendix B: Study Visits and Master Schedule*:

Assessment / Procedure	Screening Assessments	7 Days Prior to implant	Implantation	Adjustment	Explantation	Follow-Up Assessment weeks 1-32	WEEKS 36 - 56
Informed Consent	X						
Date of birth/gender	X						

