Body Weight	X	X	X	X	X	X	X
Body Height	X						
BMI	X	X	X			X* (week 32)	X * (week 56, or 24 weeks after extraction)
Ideal weight/ Excess Weight	X				X	X* (week 32)	X * (week 56, or 24 weeks

Assessment / Procedure	Screening Assessments	7 Days Prior to implant	Implantation	Adjustment	Explantation	Follow-Up Assessment weeks 1-32	WEEKS 36 - 56
							after extraction)
Medical History	X						
Physical Exam 	X			X	X		Week 36, or 4 weeks after extraction
Blood Pressure	x		X	X	X	X	Week 36, or 4 weeks after extraction
CBC  Coag  (Coag @ screen only)	X						Week 36, or 4 weeks after extraction
H. Pylori Serology	X						
Chemistry Panel 	X						X Week 36, or 4 weeks after extraction
HgbA1C2 IF DIABETIC	X						X Week 36, or 4 weeks after extraction
EKG*(Females and Males >40 y/o	X						
Psychological Evaluation	X						
Inclusion and Exclusion Criteria	X						
Develop/Review Dietary Plan	X						
Satiety and Dietary Assessment						X	X (or 24 weeks after extraction)
Investigator or Nurse follow up				X	X	X	X (or 24 weeks after extraction)
Medications List	X	X				X	X Week 36, or 4 weeks

 Investigator or co-investigator must perform physical exam.

 See section 4.3.1 for required tests

Assessment / Procedure	Screening Assessments	7 Days Prior to implant	Implantation	Adjustment	Explantation	Follow-Up Assessment weeks 1-32	WEEKS 36 - 56
							after extraction
Urine Pregnancy Test women of child bearing potential*	X	X					
Adverse Events/Device Complications			X	X	X	X	X
Verify Birth Control for Females	X						

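### Birth control must be verified at follow-up, but the schedule marks that check at screening only; separately, no pregnancy test is scheduled before the week-18 volume addition

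*Combined protocol and SAP*

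**What the plan says.** Item 9 of the inclusion criteria (section 3.5.1) applies to women of childbearing potential in both arms. It lists acceptable contraceptive methods and then states: "The method of birth control must be documented and verified at follow-up". It adds that if a device-arm subject becomes pregnant while implanted, the balloon comes out in the second trimester, timed with her obstetrician.

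Screening (section 4.3.1) covers the documentation duty: "Record contraceptive method for female subjects". The same section places a urine pregnancy test at the pre-implantation visit, within 7 days of implantation, and gives the consequence of a positive result: "Subjects with a positive pregnancy test or who are taking medications listed in the exclusion criteria will be excluded from the study".

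Section 4.3.4 sets out follow-up in two ways. A list headed "Each follow-up visit will include" has four items: clinical assessment; satiety and dietary assessment; adverse events, device complications and concomitant medication; and weight. A table follows, introduced as "A summary of required visits and procedures for subjects who do not require an unscheduled endoscopy". It has one row labelled "Verify Birth Control for Females" and one labelled "Urine Pregnancy Test women of child bearing potential".

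At week 18 ± 4 (section 4.3.3.2.5, subsection 4), subjects who still have a balloon are evaluated for an upward adjustment. After two exemptions the algorithm reads: "For all other subjects, endoscopy will be performed, and adjustments/treatment decisions will reflect the following algorithm". The procedure is an endoscopy under the sedation used at implantation. Section 4.3.3.2.7 has a failed balloon replaced with a new one unless that is against the patient's interest.

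**The concern.** Item 9 sets two duties, to document and to verify, and only the first has a place in the visit procedures. Sites work from the schedule. A site could complete every marked cell and every listed item and still not do what the eligibility rule says must be done, and the schedule would not show anything as missed.

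The second matter is related but different in kind. Item 9's extraction instruction operates only if a pregnancy is known. After implantation the schedule contains neither a contraception check nor a pregnancy test, and the next planned intervention makes the balloon larger. Symptoms are a weak signal here, because the table of anticipated adverse events (section 6.2.2) expects nausea, vomiting and abdominal pain in nearly all balloon patients. What is at stake is the safety of a woman whose pregnancy nobody has recognised, and the protocol's agreement with itself.

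**Working it through.** The plan states no figure to reproduce. The check compares text with table, plus one interval calculation.

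**Part 1: verification of birth control**

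| Source | Documented? | Verified at follow-up? |
|---|---|---|
| Section 3.5.1, item 9 | required | required, frequency not given |
| Section 4.3.1, screening exam | yes | not applicable |
| Section 4.3.4, list of follow-up visit content | not applicable | absent |
| Section 4.3.4, table | one mark, under Screening | Follow-Up weeks 1-32 column blank |

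The table has seven columns: Screening, 7 Days Prior, Implantation, Adjustment, Explantation, Follow-Up weeks 1-32, and Weeks 36-56. The verification row has a single mark, in the first. The column that matters is weeks 1-32, which covers the implant period and the whole of control follow-up.

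A mark lost or shifted in the text extraction is an unlikely explanation. Nearby rows keep their blank cells. The adverse-event row, for example, is blank in the first two columns and marked in the last five.

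Because item 9 gives no frequency, one later check would satisfy it. None is scheduled.

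Concomitant medication, recorded at each follow-up visit, could reveal hormonal methods. It would not reveal diaphragms, condoms or abstinence, all of which item 9 accepts.

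**Part 2: interval without a scheduled pregnancy test**

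Inputs: the last scheduled test is 0 to 7 days (0 to 1 week) before implantation (sections 4.3.1 and 4.3.4); the adjustment is at week 18 ± 4 (section 4.3.3.2.5). Weeks are counted from implantation.

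- Shortest gap: (18 − 4) + 0 = 14 weeks
- Longest gap: (18 + 4) + 1 = 23 weeks

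The pregnancy-test row is marked at Screening and at 7 Days Prior, and the Adjustment column is blank.

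The exemptions were then read one by one:

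- No endoscopy at week 18: goal weight reached without reflux, gastritis or ulcer symptoms; or a gastric ulcer at an earlier unscheduled endoscopy.
- No adjustment: erosive gastritis, small ulcers, or grade 1-2 esophagitis at an earlier unscheduled endoscopy.
- No volume addition: ulceration, erosive gastritis or esophagitis found at the week-18 endoscopy, or reflux not controlled by medication.

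Pregnancy appears in none of them. A subject who meets no exemption receives 200, 250 or 300 ml according to height, reflux and any earlier volume reduction, subject to the 1,000 ml maximum.

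For replacement of a failed balloon, section 4.3.3.2.7 states no repeat test, although pregnancy bars enrolment (section 3.5.2, criterion 24) and a positive test excludes the subject before the first implant.

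**Upper bound on added tests at adjustment:** 188 device-arm subjects × 1 = 188. This would be reached only if every one were a woman of childbearing potential who came to adjustment.

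**The case against.** The strongest reply to the first part is that item 9 is already binding, a summary table cannot cancel an eligibility rule, and follow-up visits are recorded on CRF6 and CRF7, which were not available. If those forms, or Appendix B, carry a contraception field, sites would be prompted to verify. That stands as a limit on the practical consequence. It does not remove the mismatch in the protocol body, where a row named for this very check is marked only at screening.

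On the second part, a reader might infer that the protocol breaks its own rule by not repeating the pregnancy test. It does not: no text promises a repeat test, so this is an omission and the proposed test is an addition. A reader might also infer that item 9 wants the balloon out as soon as pregnancy is detected, or that it would spare a pregnant woman sedation. Neither follows. Extraction is set for the second trimester, and it is itself done under conscious sedation (section 4.3.3.2.6). What remains is narrower: volume added, or a new balloon placed, in an unrecognised pregnancy.

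Existing controls narrow it further. Contraception is a condition of entry; visits after week 4 are every 4 weeks within a ± 2 week window and include a clinical assessment; a physical exam is marked at Adjustment; the addition must be judged clinically appropriate; and replacement is subject to a best-interest clause. These would probably catch a known pregnancy. None is designed to find an unknown one.

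Blank cells should not be over-counted. The post-explant column, and the implantation column that follows a test by at most 7 days, are not places where a further check is being asked for.

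**Conclusion.** The inconsistency holds: a mandatory follow-up check in section 3.5.1 is scheduled at screening only in section 4.3.4 and is missing from the list of follow-up visit content. It is minor, and it rests on the protocol body alone, since the follow-up forms and Appendix B were not available.

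The pregnancy-test gap is real but separate. It is a safety improvement worth making at the same time, not a contradiction. Its size is 14 to 23 weeks without a scheduled test before a possible 200-300 ml addition, counting weeks from implantation. The pregnancy-test row label carries an asterisk with no note in the supplied text; a note there could add a condition.

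The documents give no pregnancy rate, so the number of women affected cannot be estimated. A reader might infer some effect on the weight-loss results. Nothing in the documents supports that, and the point does not touch sample size, power, type I error or the co-primary analyses.

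**What to change.** **To correct the inconsistency**

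- In the section 4.3.4 table, and in Appendix B if it carries the same table, mark the birth-control verification row in the Follow-Up weeks 1-32 column.
- Add the check to the section 4.3.4 list of follow-up visit content, for women of childbearing potential in both arms.
- Confirm that CRF6 and CRF7 have a field for it.

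**As an inexpensive safety addition**

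- Mark a urine pregnancy test for women of childbearing potential in the Adjustment column, to be done before the endoscopy.
- Add a line to the week-18 algorithm in section 4.3.3.2.5: a pregnant subject receives no volume addition and is managed under item 9.
- Add a sentence to section 4.3.3.2.7 requiring a negative test before a replacement balloon is placed.

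The cost is two table marks, one list item, one algorithm line and one sentence. It adds about one urine test per device-arm woman of childbearing potential, at most 188, plus one per replacement. The trial already uses this test, and the analysis is unchanged.

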#### **3.5.2. Exclusion Criteria**

1. Prior gastrointestinal surgery with sequelae, i.e. obstruction, and/or adhesive peritonitis or known abdominal adhesions.
2. Prior open or laparoscopic bariatric surgery.
3. Prior surgery of any kind on the esophagus, stomach or any type of hiatal hernia surgery.
4. Any inflammatory disease of the gastrointestinal tract including esophagitis, Barrett's esophagus, gastric ulceration, duodenal ulceration, cancer or specific inflammation such as Crohn's disease.

5. Potential upper gastrointestinal bleeding conditions such as esophageal or gastric varices, congenital or acquired intestinal telangiectasis, or other congenital anomalies of the gastrointestinal tract such as atresias or stenoses.
6. A gastric mass.
7. A hiatal hernia > 2cm or severe or intractable gastro-esophageal reflux symptoms.
8. Acid reflux symptoms to any degree that require more than one medication for symptom control.
9. A structural abnormality in the esophagus or pharynx such as a stricture or diverticulum that could impede passage of the balloon alongside the endoscope.
10. Achalasia or any other severe esophageal motility disorder that may pose a safety risk during the removal of the device
11. Severe coagulopathy.
12. Insulin-dependent diabetes (either Type 1 or Type 2) or a significant likelihood of requiring insulin treatment in the following 12 months.
13. Subjects with any serious health condition unrelated to their weight that would increase the risk of endoscopy
14. Chronic abdominal pain
15. Motility disorders of the GI tract such as gross esophageal motility disorders, gastroparesis or intractable constipation
16. Hepatic insufficiency or cirrhosis
17. Serious or uncontrolled psychiatric illness or disorder that could compromise patient understanding of or compliance with follow up visits and removal of the device after 8 months.
18. Alcoholism or drug addiction.
19. Patients unwilling to participate in an established medically-supervised diet and behavior modification program, with routine medical follow-up.
20. Patients receiving daily prescribed treatment with aspirin, anti-inflammatory agents, anticoagulants or other gastric irritants.
21. Patients who are unable or unwilling to take prescribed proton pump inhibitor medication for the duration of the device implant.
22. Patients who are known to have, or suspected to have, an allergic reaction to materials contained in the system.
23. Patients who have ever developed a serotonin syndrome and are currently taking any drug known to affect the levels of serotonin in the body [e.g., selective serotonin reuptake inhibitors (SSRIs), serotonin-norepinephrine reuptake inhibitors (SNRIs), monoamine oxidase inhibitors (MAOIs)] should not undergo placement of the device.
24. Patients who are pregnant or breast-feeding.

25. Subjects with Severe cardiopulmonary disease or other serious organic disease which might include known history of coronary artery disease, Myocardial infarction within the past 6 months, poorly-controlled hypertension, required use of NSAIDs
26. Subjects who have tested positive for H. Pylori.
27. Subjects taking medications on specified hourly intervals that may be affected by changes to gastric emptying, such as anti-seizure or anti-arrhythmic medications
28. Subjects who are taking corticosteroids, immunosuppressants, and narcotics
29. Subjects who are taking diet pills
30. Use of an intragastric device prior to this study due to the potential increase in risk associated with implantation of a balloon in a previously instrumented and possibly scarred stomach.
31. Participation in any clinical study which could affect weight loss within the past 6 months due to the potential to confound findings.
32. Symptomatic congestive heart failure, cardiac arrhythmia or unstable coronary artery disease.
33. Pre-existing respiratory disease such as chronic obstructive pulmonary disease (COPD), pneumonia or cancer.
34. Diagnosis of autoimmune connective tissue disorder (e.g. lupus, erythematous, scleroderma) or immunocompromised.
35. Life expectancy less than 1 year or severe renal, hepatic, pulmonary or other medical condition, in the opinion of the investigator because of an increased risk profile.
36. Specific diagnosed genetic or hormonal cause for obesity such as hypothyroidism or Prader Willi syndrome
37. Eating disorders including night eating syndrome (NES), bulimia, binge eating disorder, or compulsive overeating
38. Known history of endocrine disorders affecting weight

